4.2.4. Spectrogram and Mel-spectrogram Extraction

Spectrograms of each of these WAV (waveform audio file format) audio files will be computed to obtain a visual representation of the spectrum of audio frequencies against time¹⁵. The spectrogram will be log-transformed, converting it from an amplitude representation to a decibel representation. Spectrograms are generated by performing the Short-Time Fourier Transform (STFT) with a sliding Hamming or Hann window. Examples of

parameters are sliding window size 32ms, hop window of 10ms, and a 512-point Fast Fourier Transform (FFT). This would give spectrograms of size 257 x 201 for 2 seconds of audio data recorded with a 16k Hz sampling rate. The resulting spectrogram will be integrated into Mel-spaced frequency bins (such as 64), where the magnitude of each bin is log transformed¹⁶. The Mel spectrogram has the advantage over a typical frequency spectrogram because the Mel scale in the Mel spectrogram has unequal spacing in the frequency bands and provides a higher resolution in lower frequencies, as compared to the equally spaced frequency bands in a normal spectrogram.

The Mel spectrogram follows speech recognition systems. The lower coefficients which map to the lower frequencies associated with human hearing capabilities will be examined. There are several methods for converting the frequency scale to the Mel. One way to convert frequency f into Mel scale m as¹⁷:

$$m = 2595 \times \log_{10}\left(1 + \frac{f}{700}\right)$$

Cepstral analysis will be performed on the Mel spectrum of audio samples to compute their Cepstral coefficients, so called Mel Frequency Cepstral Coefficients (MFCC)¹⁷. The extracted MFCC features result in a two-dimensional matrix for every sample, where each column represents one signal frame, and each row represents extracted MFCC features for a specific frame. MFCC features can be used in several ways for classification. Spectrograms, Mel spectrograms and MFCC will be used as input to the Deep Learning Modeling described in Section 4.2.6^{18,19}.

4.2.5. Classical Machine Learning

Using the reduced feature set from Section 4.2.3., classical machine learning algorithms will be trained to perform the binary classification of well versus sick states. Ensemble learning algorithms are the preferred method because they: typically generalize well, are very robust to overfitting, can be trained efficiently, require little hyper-parameter tuning to achieve competitive results, perform predictions quickly and can be easily packaged for deployment²⁰. The classical machine learning approach also lends itself to making understandable predictions. SHapley Additive exPlanations (SHAP)²¹ will be used to investigate the most successful models to determine to what degree each feature influences model output. The main classical machine learning models of interest include: Random Forest²²; Bagging²³; Extreme Gradient Boosting (XGBoost)²⁴; Light Gradient Boosting Machine (LGBM)²⁵; Support Vector Machine (SVM) Ensemble²⁶.

Additional modeling may include a combination of spectrograms (described in Section 4.2.4.) and voice features described in Section 4.2.2. The spectrogram averaged across time may be combined with the voice features and used as the input to the classical machine learning model. In early fusion, a classifier is trained on the combined set of voice features and averaged spectrograms. In late fusion, separate models are trained on averaged spectrograms and voice features, and the final prediction is the average of the output from the two models²⁷⁻²⁹.

In addition, covariance approach which quantifies the linear relationship between features will also be explored to perform the binary classification of well versus sick states. This

approach has been shown to be invariant to the linear transformation of the features³⁰. This invariance property might diminish the intersubject variability of the acoustic features and can also reduce any learning effects of the acoustic features over time on the model performance. The input data for this approach will be the MFCCs matrix, as described in [Section 4.2.4](#).

Specifically, the covariance matrix between MFCCs will be estimated using the Ledoit-Wolf shrinkage estimator.³¹ Each covariance matrix is an instance of symmetric positive definite matrix and represents a point on the Riemannian manifold.³² To apply classical distance-based machine learning algorithms, the resulting covariance matrix can be mapped to the tangent space³³ which is an instance of a vector space. This transformation to the tangent space also permits the fusion of other acoustic features in the covariance model. Finally, classical machine learning models like Random Forest²²; Balanced Random Forest³⁴, Bagging²³; Extreme Gradient Boosting (XGBoost)²⁴; Light Gradient Boosting Machine (LGBM)²⁵; Support Vector Machine (SVM) Ensemble²⁶ will be explored in the tangent vector space to perform the binary classification of well versus sick states.

4.2.5.1. Classical Machine Learning Model Training and Testing

The data will be randomly divided into two sets by subject: training (e.g., 80% of subjects) and test set (e.g., 20% of subjects). Repeated stratified k-fold cross validation (on the subject level) on the training data will be used to evaluate performance, as it provides confidence in the resulting performance values. Both k (number of folds) and n (number of repetitions) will be chosen based on the final sample size. The test set will be a hold-out test set until model training and validation is complete.

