4. GENERAL METHODOLOGY AND CONVENTIONS

4.1. Hypotheses and Decision Rules

Given the algorithm's intended use as a screening tool in the general population not guided by a healthcare professional, we would define the success criteria for the algorithm as achieving a sensitivity on par with that of a rapid antigen test for SARS-CoV-2 infection as observed in real world studies, which is between 60% and 80%¹. Hence, the success criteria for the algorithm will be an observed sensitivity of 70% or better.

The specificity of the algorithm will be assessed with a target minimum specificity of 60% as observed in other studies that use audio signals to detect SARS-CoV-2 infection². The goal is to optimize the sensitivity of the algorithm as the primary performance measure without compromising the minimum specificity, since this algorithm is meant to be used as a screening tool (high sensitivity) and not a diagnostic tool. The reference rapid antigen test benchmarks compared to RT-PCR test for SARS-CoV-2 are as follows¹: sensitivity $\geq 80\%$ in symptomatic individuals and sensitivity $\geq 60\%$ in asymptomatic individuals.

The probability that the observed sensitivity for symptomatic RT-PCR positive participants in AcRIS is greater than 70% with a total number of 100 cases is given in the following table for two assumed true values of expected sensitivity.

Table 1. Probability that observed sensitivity in symptomatic RT-PCR positive participants in AcRIS is greater than 70% with total of 100 cases.

[figure not shown]
True Sensitivity	Probability of Observed Sensitivity > 70% ¹
60%	0.02
75%	0.88
80%	0.99

Thus, with at least 100 symptomatic RT-PCR positive participants in AcRIS, we hypothesize that the study has high probability of success under these conditions.

Furthermore, Figure 1. illustrates the number of cases required to achieve target sensitivity values for a given screening tool – e.g., for a sensitivity of 70% with 10% margin of error for the 95% confidence interval (i.e., 60% to 80%), 81 cases are required (assuming a binomial distribution for the sensitivity values). Identifying 100 symptomatic positive cases should allow us to attain 70% target sensitivity with precision of 8.98%.

¹ Under the assumption of a binomial distribution.

Figure 1. Estimation of the number of cases required to achieve target sensitivity values assuming a 10% margin of error.

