5. ANALYSES AND SUMMARIES

5.1. Classification of Well and Sick States using Classical Machine Learning Models

- Analysis Set: Participants in Primary Analysis Set ([Section 3](#)).
- Statistical Method: Classical machine learning modeling will be performed as described in [Section 4.2.5](#). The best performing model will be selected based on performance metrics listed in [Section 4.2.5.2](#).

- Summaries:

Using the output of the best performing model described in [Section 4.2.5.3](#), the following results will be generated for the specified analysis set (data permitting):

- Listing of the features used in the final model
- Summary statistics of the performance measures listed in [Section 4.2.5.2](#). (mean and standard deviation) for classification of sick and well states for the validation set. Results will be presented in a table.
- The confusion matrix for the test set will be tabulated and a listing of the performance measures provided.

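### The algorithm's performance is reported with a resampling SD for validation and no interval for the hold-out, so the sampling error around the 70% sensitivity criterion is never shown.

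*SAP*

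**What the plan says.** All section numbers are in the adSAP unless stated.

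- **Criterion (4.1).** "the success criteria for the algorithm will be an observed sensitivity of 70% or better". Support comes from Table 1 ("Probability that observed sensitivity in symptomatic RT-PCR positive participants in AcRIS is greater than 70% with total of 100 cases") and from a precision statement: "for a sensitivity of 70% with 10% margin of error for the 95% confidence interval (i.e., 60% to 80%), 81 cases are required", and 100 cases "should allow us to attain 70% target sensitivity with precision of 8.98" percent. The conclusion of a high chance of success is drawn "with at least 100 symptomatic RT-PCR positive participants in AcRIS".
- **Classical models (4.2.5.1, 4.2.5.2).** Subjects are split at random, with 80% training and 20% test as the example. Repeated k-fold cross-validation on the training part "will be used to evaluate performance, as it provides confidence in the resulting performance values". The numbers of folds and repeats are left open. The chosen model is refitted on all training data, and the hold-out gives the final results. Table 2 counts predictions, not participants.
- **Deep learning (4.2.6.3 to 4.2.6.5).** The example split is 70/10/20. The training/validation split is replicated three times at subject level; this is not repeated k-fold.
- **Reporting (5.1; same pattern in 5.2 to 5.4).** Summary statistics ("mean and standard deviation) for classification of sick and well states for the validation set"), and for the hold-out: "The confusion matrix for the test set will be tabulated and a listing of the performance measures provided".
- **Further testing (5.5.1, 5.5.2).** Confusion matrix, listing, and tables and plots by symptom threshold, without intervals.

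The only interval in the readable adSAP is the planning one in 4.1. The 90% CIs in main SAP 5.2.2.3 to 5.2.2.5 belong to the symptom and voice-feature models.

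**The concern.** Two different things can be mistaken for precision here, and neither describes the result that matters.

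First, the validation SD. Repeats reuse the same participants, so an SD over repeats reflects how folds happened to be drawn. An SD over folds is the spread among small subsets. An SD over three deep learning splits rests on three values. None of these is the uncertainty of sensitivity in new participants, and the plan does not say at which level the SD is taken.

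Second, the planning figure. The ±8.98 points belong to 100 cases, while the final result comes from about a fifth of them.

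A hold-out sensitivity near 70% would be set against the criterion with no sign of how far chance alone could have moved it. A reader could not supply the missing interval, because the published matrix counts predictions and the sick window can span several days per participant.

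**Working it through.** **1. The plan's own figures (4.1), for p = 0.70.**
- Cases for ±10 points: n = 1.96² × 0.70 × 0.30 / 0.10² = 80.7, so 81. Stated: 81.
- Half-width with 100 cases: 1.96 × √(0.21/100) = 8.98 points. Stated: 8.98.
- Table 1 by normal approximation: 0.021, 0.876, 0.994 for true sensitivity 60%, 75%, 80%. Stated: 0.02, 0.88, 0.99.

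The planning arithmetic is sound for 100 independent cases.

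**2. The same formula for the hold-out, one result per participant.** Input: 20% of 100 cases = 20. The 20% is only an example in 4.2.5.1, so a range is shown.

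| Test cases | 1.96 × √(0.21/n) |
|---|---|
| 15 | ±23.2 points |
| 20 | ±20.1 points |
| 30 | ±16.4 points |
| 100 (as in 4.1) | ±8.98 points |

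For 14 of 20 detected (70%), the Clopper-Pearson 95% interval is 45.7% to 88.1% and the Wilson interval 48.1% to 85.5%.

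**3. Chance of meeting the criterion (observed ≥70%).** Exact binomial:

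| True sensitivity | 100 cases, ≥70 | 20 cases, ≥14 |
|---|---|---|
| 60% | 0.025 | 0.25 |
| 75% | 0.896 | 0.79 |
| 80% | 0.994 | 0.91 |

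**4. Several recordings per participant.** Assumed, because the documents give no figures: mean sensitivity 0.70, between-participant SD s of 0.20 to 0.35, and m = 5 to 8 sick recordings each. The variance of the hold-out sensitivity is [s² + (0.21 − s²)/m] / 20.
- s = 0.20, m = 8: (0.040 + 0.02125)/20 = 0.00306, SE 5.5 points, half-width 10.8.
- s = 0.35, m = 5: (0.1225 + 0.0175)/20 = 0.0070, SE 8.4 points, half-width 16.4.
- With the t quantile on 19 degrees of freedom (2.093) these become 11.6 and 17.5.

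So the half-width is about 11 to 17 points. A simple binomial interval from the prediction-level matrix would be too narrow: 20 participants × 5 recordings = 100 predictions gives ±8.98 again, against 11.9 (s = 0.20) to 16.4 (s = 0.35) from the clustered formula.

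**5. What the cross-validation SD measures.** Illustrative simulation, all settings assumed: 80 training participants, one well and one sick record each, nearest-mean classifier on 10 features, 20 repeats, 400 simulated studies, mean sensitivity about 65%.

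| | k = 5 | k = 10 |
|---|---|---|
| True SD of the estimate across studies | 4.0 points | 4.1 points |
| Mean SD over folds | 11.9 | 16.7 |
| Mean SD over repeat averages | 2.4 | 1.9 |

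Ratios to the true SD: folds 3.0 and 4.1; repeats 0.62 and 0.46. The reported SD therefore changes with k and with the level at which it is taken, and matches the sampling error at neither level.

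**The case against.** - **The SD is offered only as a summary statistic.** This stands. No section calls it a standard error or uses it to judge the 70% criterion. A reader might infer from the wording in 4.2.5.1 that the plan treats the SD as precision, but the text does not go that far. The fault is the missing label and the missing interval.
- **Repeats are not pooled.** A reader might infer from 4.2.5.3, which keeps all predictions from the repeated cross-validation, that repeats will be stacked and counted as independent. No section plans this or derives a standard error that way, so no such error can be charged to the plan.
- **Precision is stated.** True for planning: 4.1 gives 8.98 points and the figure is correct. It does not carry over to the hold-out.
- **The criterion needs no interval.** Also true. It is a rule on the observed value, the study is exploratory, and main SAP 5.1 says it will make no decision rules. Yet 4.1 does define success and argues for it with a 95% interval, so reporting the achieved interval is consistent with that argument.
- **The hold-out is not the only evidence.** Section 5.5.2 also tests sensitivity on symptomatic participants positive at swab #1. That result has no interval either.
- **Every ratio depends on assumptions.** Correct: k, the number of repeats and the split are open. The direction does not depend on them, and 15 to 30 test cases lead to the same conclusion.

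**Conclusion.** The point holds. In the readable adSAP the validation result carries a resampling SD that does not estimate sampling error, and the hold-out result carries nothing. With about 20 hold-out cases the 95% half-width at 70% is about ±20 points with one result per participant, or about ±11 to ±17 under the clustering assumed above, against the ±8.98 stated for 100 cases. With one result per participant, an algorithm with true sensitivity 60% would meet the criterion on the hold-out about one time in four.

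Limits:
- The 20 cases follow from an example split of the planned 100.
- The plan does not say whether the 70% is judged on cross-validation or hold-out data. If on cross-validation, 80 training cases would give ±10.0 points with one result each, before any allowance for model selection.
- The simulated ratios are illustrative. They cover repeated k-fold, not the three deep learning splits, where the SD has even less to rest on.
- Parts of the adSAP are redacted, so the absence of intervals is established for the readable text only.

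A reader might go further and conclude that the planning figures are wrong or that the criterion cannot be applied. Neither follows: the figures reproduce for 100 cases, and a point-estimate rule can be applied as written. What is missing is the uncertainty needed to interpret the outcome.

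**What to change.** 1. In 4.2.5.2, 4.2.6.4 and Sections 5.1 to 5.5, report sensitivity and specificity on the hold-out and on the further test sets, with 95% CIs from a bootstrap that resamples participants and keeps each participant's recordings together. Add balanced accuracy and AUC where both classes are present. Secondary Set A has only well-state data and Set B only sick-state data, so these two measures do not apply there.
2. In 4.1, state which data set the 70% criterion applies to, and show the sensitivity CI next to it. Note that 8.98 points and Table 1 describe 100 cases, and give the figures for the expected hold-out size.
3. Label the validation SD as resampling variability, say whether it is over folds, repeats or the three splits, and reword the claim in 4.2.5.1 about confidence in the values.
4. Optional: average each recording's out-of-fold predictions over repeats and bootstrap participants. This evaluates an ensemble rather than the single final model and omits training and selection variability, so it should not replace the hold-out interval.

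Cost: SAP wording and a short program on predictions that 4.2.5.3 and 4.2.6.5 already keep with their labels (participant identifiers must be kept too). No new data or design change. The downside is that the stated precision will look less favourable than 4.1 suggests.

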4.2.5.2. Classical Machine Learning Model Selection

In order to evaluate model performance, predictions from each model will be summarized in a confusion matrix, as shown in Table 2. Performance metrics including *sensitivity*, *specificity* and *balanced accuracy* will be computed as shown in Table 3. Area under the receiver operating characteristic curve (AUC-ROC) showing *sensitivity* vs. $1 - \textit{specificity}$ will also be assessed. A proposed classical machine learning model will be chosen based on the repeated stratified k-fold cross validation performance. This model may be further tuned to maximize performance, will be trained on the entire training set to generate a final model, and will finally be tested on the hold-out test set to generate the final performance results.

Table 2. Confusion Matrix. True Positives (TP), True Negatives (TN), False Positives (FP), False Negatives (FN); in terms of total number among predictions.

		Actual	
		Positive	Negative
Predicted	Positive	TP	FP
	Negative	FN	TN

Table 3. Definition of Performance Measures. True Positives (TP), True Negatives (TN), False Positives (FP), False Negatives (FN).

Performance Measure	Formula
Sensitivity	$TP / (TP + FN)$
Specificity	$TN / (TN + FP)$
Balanced Accuracy	$(\text{Sensitivity} + \text{Specificity}) / 2$

4.2.5.3. Classical Machine Learning Model Output

The final output of the classical machine learning approach will be the full set of model predictions for the best-performing model's repeated k-fold cross-validation, as well as the full set of predictions of this model on the hold-out test set. Both sets of predictions will be paired with their respective labels so that all performance metrics can be calculated.

4.2.6. Deep Learning

[figure not shown]
In addition to classical machine learning algorithms, deep learning models will be used to perform the binary classification of well versus sick states. The input data for the deep learning models will include spectrograms, Mel-spectrograms, or other variants of spectrogram such as log-Mel-spectrogram or MFCC, as described in [Section 4.2.4](#) for the CNN models or the audio files in case of Transformer models.

Deep learning models have been widely used to classify covid positive and negative participants using voice or cough data (e.g., see review papers by Deshpande et al ³⁵ and Qian et al, ³⁶). Most studies have used various architectures of convolutional neural network (CNN) models, and few have applied recurrent neural networks (RNN) ³⁷. More recently, Transformers have been found useful for speech analysis ^{38,39}. We may apply various architectures of the CNN models such as ResNet18 (Residual Neural Network 18) ⁴⁰, VGG16 (Visual Geometry Group 16) ⁴¹, VGG19 ⁴² or custom built models.

We will choose the CNN architectures based on the dimension of the final dataset. The details of the CNN architectures that may be computed are as follows:

[figure not shown]
ResNet18: ResNet-18 is a convolutional neural network that is 18 layers deep (Figure 2). ResNet is more recent architecture than original CNN architectures like VGG. The advantage of ResNet is the skip connections, or shortcuts to jump over some layers. One of the problems of deep neural networks is that the first layers' weights will not change much during the training process. This is called vanishing gradient. The skip connections solve the problem of vanishing gradients in deep neural networks by allowing this alternate shortcut path for the gradient to flow through. These connections also help by allowing the model to learn the identity functions which ensure that a higher layer will perform at least as well as the lower layer, and not worse. Layers may be added or removed based on our data. Cross-validation will be used to determine if the model is overfitting the training data. In that case, layers will be removed to reduce the complexity of the model. If the model is underfitting the data, more layers will be added.

Figure 2. ResNet18 architecture. Conv stands for convolution; FC is fully-connected layer and SoftMax is the activation function used in the last layer. The last layer will be adjusted using a sigmoid function for a binary classification. Figure source: Ramzan et al., 2019⁴³.

[figure not shown]
VGG16: VGG16 is a simple and widely used CNN architecture with 16 layers depth (Figure 3), which was originally built for ImageNet, a large visual database project used in visual object recognition software research. VGG16 is popular due to its ease of implementation and is used in many deep learning image classification techniques. Recently, VGG16 and VGG19 has been used for classifying SARS-CoV-2 infection positive and negative individuals using voice data ^{42,44}. Layers may be added or removed based on our data.

Figure 3. VGG16 architecture. Figure source: <https://neurohive.io/en/popular-networks/vgg16/>

State-of-the-art architectures: Studies ^{19,45,46} using state-of-the-art CNN architectures which are less dense (<10 layers) than typical standard CNN models (>16 layers), have been shown to be successful for SARS-CoV-2 classification as well. Therefore, CNN architectures that do not follow standard architectures (e.g., ResNet or VGG) will be built. This allows for the choosing/adjustment of the number of layers, kernel size, filter size, padding, stride, pooling type and size, batch normalization, and number of nodes in the fully connected layer based on the classification task. Dropout will be used at various layers for regularizing the parameters to help prevent the neural network from overfitting ⁴⁷. Lastly, we might add Long Short-Term Memory layer to the CNN model which will help to find temporal relationships ⁴⁸. A schematic display of a conventional CNN architecture is shown in Figure 4.

Figure 4. Example CNN model with three convolutional layers followed by fully connected layer. The last layer is the classification layer which has only two nodes with sigmoid function as the activation function. Figure adapted from Kulchyk et al, 2019⁴⁹

In addition to the above described modeling, we may try two open source, Transformers-based acoustic models that use audio files as the input.

The first model is the Nvidia Connectionist Temporal Classification model⁵⁰, an encoder-decoder based transformer model originally developed as a speech-to-text model trained on thousands of hours of human speech. The pretrained encoder model will be used to generate acoustic features and develop a classification algorithm to predict whether a participant is sick or well.

The second model is Wav2vec2³⁸ way, a self-supervised, deep-learning transformer model which learns latent encodings of audio recordings using contrastive predictive coding tasks. A custom wav2vec2 model will be trained on the reading task and a deep-learning classification model will be trained to predict whether a participant is sick or well.

